2.1 Data analysis general information

Summary statistics for continuous variables will include N, mean, standard deviation, minimum, lower quartile, median, upper quartile, maximum. Summary statistics for discrete variables will be presented in contingency tables and will include absolute and relative frequencies.

If not otherwise specified, p-values will be presented as one-sided for hypotheses testings and as two-sided for other analysis. The level of significance will be set to 2.5% (one-sided, family-wise type-I-error). 95% confidence intervals will be displayed but not be used for decision making; they will only be used for estimation and will therefore always be two-sided.

All listings will be presented by treatment sequence.

Footnotes on outputs will be kept to a minimum also for outputs not covered in [REDACTED].

Footnotes will generally be provided for

- abbreviations used in the output; abbreviations used on several outputs, e.g. for listings in [Appendix 16.2](#) can be presented on a separate page and do not have to be repeated as footnotes on each listing
- sorting order of categories, e.g. for sorting within MedDRA (Medical Dictionary for Regulatory Activities) hierarchy levels

- MedDRA version used for reporting of MedDRA coded data

Footnotes will generally NOT be given for

- units displayed on the output
- interpretation of results (e.g. “odds ratio larger 1 favors active treatment”)
- information that can be retrieved from the statistical section of the clinical study report (CSR) unless it is not identifiable from the output, e.g.
 - explanation of analysis model used unless results of more than one model are displayed on an output
 - derivations of variables (e.g. BMI will not be explained on a footnote)
- information that will be provided in the clinical study protocol and/or methods section of the CSR (e.g. baseline definition if this is specified in the statistical section of the CSR)

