5.4 Statistical models

5.4.1 Primary analysis

5.4.1.1 Logistic regression

Binary outcome variables, including PASI [REDACTED] / 90 / [REDACTED] response and IGA mod 2011 0 or 1 response, will be evaluated using a logistic regression model with treatment regimen, body weight stratum and baseline PASI score. Odds ratios will be computed for comparisons between treatment groups utilizing the logistic regression model fitted.

If response rates are 0% or 100% in one of the treatment groups odds ratio estimate and p-values will not be displayed in outputs, but “-” will be shown.

The odds ratio will be calculated such that an odds ratio >1 is favorable for secukinumab. Using PROC GENMOD to calculate the confidence interval for the odds ratios assumes asymptotic normality of the Wald estimate for the regression coefficient. The 95% confidence interval for the regression parameter of the active treatment effect relative to control(s) will be calculated using an exponential transformation to create the confidence interval for the odds ratio.

All p-values reported on linear hypotheses about regression coefficients will be based on the Wald tests from Type III analyses. In the SAS procedure PROC GENMOD, a Type III analysis will be performed by adding the model options: TYPE3, DIST=BIN, and LINK=LOGIT.

Logistic regression will be applied to response variables at each visit.

If logistic regression model does not converge the following steps will be performed:

1. If convergence not reached, remove the covariates from the model one by one until convergence is reached; start with removing baseline body weight, followed by baseline PASI;
2. If convergence not reached, perform Fisher's exact test.

It should be noted that this model might not converge if response rates are too low.

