ODS OUTPUT Estimates=Estimates;  
RUN;
```

The MIANALYZE procedure expects the parameter estimate in the variables ESTIMATE, and the corresponding standard error in the variable STDERR. Measurements can be obtained from "Estimates" dataset by selecting the row with ODDS ratio estimates.

```
Data <modified dataset>;  
set Estimates;  
if substr(label,1,3)= "Exp";  
ESTIMATE=LBetaEstimate;  
STDERR=StdErr;  
effect= "OR";  
if missing(ESTIMATE) or missing(STDERR) then delete;  
RUN;
```

The estimates and standard errors based on the 100 imputed data are then combined by applying Rubin's rules for multiple imputed data sets, see [Little and Rubin \(2002\)](#).

Programming notes:

- The variables ESTIMATE and STDERR in the input data set for the MIANALYZE procedure may not be missing. Records with missing values need to be deleted and the variable `_IMPUTATION_` needs to be renumbered and regenerated since for each by-group the procedure expects consecutive numbers starting at 1.
- The ESTIMATE and STDERR in terms of odds ratios from logistic regressions will be transformed to follow a normal distribution before MIANALYZE procedure. They will be transformed back to Odds Ratio to get the corrected ESTIMATE and corresponding CIs.

The SAS procedure MIANALYZE will be applied as follows:

Step 1:

```
DATA <modified dataset_t>;  
  SET <modified dataset>;  
  estimate=log(ESTIMATE);  
  stderr=(log(LBETAUPPERCL)-log(LBETALOWERCL))/(2*1.96);  
RUN ;  
  
ODS LISTING CLOSE;  
ODS OUTPUT ParameterEstimates=<results> VarianceInfo=<varinfo> ModelInfo=<modelinfo>;  
PROC MIANALYZE PARMS=<modified dataset>;  
  BY <by-variables>;  
  MODELEFFECTS estimate;  
  Stderr stderr;  
RUN;  
ODS LISTING;  
  
data <results_back>;  
  set <results>;  
  estimate=exp(ESTIMATE);
```

```
LCLMEAN=estimate*exp(-1.96*stderr);
UCLMEAN=estimate*exp(+1.96*stderr);
RUN ;
```

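### SAP 5.4.1.2: the pooling code for the primary analysis reads the untransformed odds-ratio data set, so as printed it reports exp(OR) instead of the OR

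*SAP*

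**What the plan says.** Multiple imputation is the primary missing-data method (SAP 2.5.5), and SAP 5.4.1.2 gives the only pooling code for the primary endpoint (H1) and the key secondary endpoint (H2). A logistic model is fitted to each of 100 imputed data sets. The code keeps the exponentiated row of the output, which the text identifies as the odds-ratio row, in `<modified dataset>`.

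A programming note then says that these values "will be transformed to follow a normal distribution before MIANALYZE procedure", and afterwards "They will be transformed back to Odds Ratio to get the corrected ESTIMATE and corresponding CIs".

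Step 1 of the listing opens with "DATA <modified dataset_t>" and writes to that data set the log of the odds ratio and a standard error derived from the log confidence limits. The next procedure is "PROC MIANALYZE PARMS=<modified dataset>". Its results go to a final data step containing "estimate=exp(ESTIMATE)" and "UCLMEAN=estimate*exp(+1.96*stderr)".

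On inference, SAP 5.4.1.1 states: "All p-values reported on linear hypotheses about regression coefficients will be based on the Wald tests from Type III analyses". SAP 2.1 states: "95% confidence intervals will be displayed but not be used for decision making".

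**The concern.** The note requires pooling on the log scale and one back-transformation. The listing creates the log-scale data set and never reads it. Pooling is done on the odds ratios, and the pooled odds ratio is exponentiated as though it were a log odds ratio. The reported figure is therefore the exponential of the mean odds ratio, and its limits are wrong in the same way.

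Two things are at stake. The first is the reported effect estimate and interval for both confirmatory endpoints. The second is the test itself. The Type III Wald tests of 5.4.1.1 come from the regression procedure, which is run separately in each imputed data set, so they give no single pooled p-value. The listing reports an estimate and limits only. The pooling output is a natural place to look for the p-value. As printed, its default null of 0 would mean testing whether the odds ratio is zero. H1 could then be rejected, and H2 opened, whichever arm is better.

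**Working it through.** **Inputs.** 165 per arm (SAP section 3); 70% PASI 90 response (Protocol 3.2, from the registration studies); a 15-point target difference (SAP section 3). Simplifications for illustration: no covariates and, at first, no missing data. The standard error in the odds-ratio row is taken to be on the odds-ratio scale, as the programming note implies.

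**Formulas.** With n = 165, p1 the every-2-weeks rate, p0 the every-4-weeks rate and q = 1 − p:

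- SE(log OR) = √[1/(n·p1·q1) + 1/(n·p0·q0)]
- SE(OR) = OR × SE(log OR)
- Intended output: OR, with limits OR × exp(±1.96 × SE(log OR))
- Output as printed: exp(OR), with limits exp(OR ± 1.96 × SE(OR))

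**Worked case, 70% vs 70%.** n·p·q = 165 × 0.7 × 0.3 = 34.65. SE(log OR) = √(2/34.65) = 0.240. OR = 1, so SE(OR) = 0.240. Intended: 1.00 (0.62–1.60). As printed: exp(1) = 2.72, with limits exp(1 ± 1.96 × 0.240) = 1.70 and 4.35.

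| Q2W vs Q4W response | SE(log OR) | Intended OR (95% CI) | As printed (95% CI) |
|---|---|---|---|
| 70% vs 70% | 0.240 | 1.00 (0.62–1.60) | 2.72 (1.70–4.35) |
| 55% vs 70% | 0.231 | 0.52 (0.33–0.82) | 1.69 (1.33–2.14) |
| 85% vs 70% | 0.276 | 2.43 (1.41–4.17) | 11.34 (3.04–42.28) |

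**When the printed interval lies above 1.** This requires OR − 1.96 × OR × SE(log OR) > 0. The odds ratio cancels, leaving 1/SE(log OR) > 1.96. The condition depends on precision alone and not on which arm is better. The same ratio is the z statistic if the printed pooling output is tested against 0: 4.16 at 70% vs 70%, 4.33 at 55% vs 70%, 3.62 at 85% vs 70%, 2.72 at 90% vs 90% and 1.98 at 95% vs 95%.

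**How often, when the arms do not differ.** All 166 × 166 pairs of binomial counts were enumerated, leaving out 0% and 100% response. The printed interval lies above 1 with probability over 99.9% at common rates of 50–85%, 99.8% at 90%, 89% at 93% and 42% at 95%. Log-scale analysis rejects in 1.9–2.7%, in line with the planned one-sided 2.5%.

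**With missing data.** The documents give no missing-data rate, so 5%, 10% and 20% were assumed. Each scenario had 2,000 simulated trials with 100 within-arm beta-binomial imputations, a simpler model than the SAP's. The printed interval lies above 1 in 100% of trials at 70% vs 70% and at 55% vs 70%, for all three rates. At 90% vs 90% the figures are 99%, 99% and 96%.

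**The case against.** The strongest reply is that the planned analysis is right and only a suffix has been dropped. The programming note specifies transforming before pooling and back afterwards. SAP 5.4.1.1 separately describes exponentiating the interval for the regression parameter to obtain the interval for the odds ratio. The listing is a template with placeholder names that a programmer must rewrite anyway. It is also unconfirmed that the call, with its combination of `PARMS=`, `MODELEFFECTS` and `STDERR`, would run at all; if it fails, no exp(OR) is produced. Confidence intervals are not used for decisions. The p-value rule in 5.4.1.1 refers to regression coefficients, which in a logistic model are log odds ratios with a null of 0, so a false rejection needs a further step that the SAP does not prescribe. Finally, an odds ratio of 2.72 beside equal response rates would be conspicuous, since the imputed response rates, risk differences and modified non-responder analysis all bypass this step.

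Most of this stands, and it limits the consequence. It does not remove the defect. The call is introduced as what will be applied, it serves both confirmatory endpoints, and no other section corrects the name. If the every-2-weeks arm does better, an inflated odds ratio in the expected direction is less likely to be questioned. The missing p-value source remains a gap whether or not the data set name is corrected.

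**Conclusion.** The concern holds. The code contradicts the note above it and, followed as printed, returns exp(OR) with limits on the wrong scale for the primary and key secondary endpoints. A null effect appears as 2.72, and a true odds ratio of 0.52 appears as 1.69 with an interval wholly above 1. These figures assume 165 per arm, unadjusted two-by-two tables, and response rates built on the protocol's 70% for the registration studies, which is not specific to subjects of 90 kg or more. They are illustrations, not forecasts for this trial.

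The wrong data set reference is certain. The wrong reported estimate is conditional on the call executing. The false-rejection risk is further conditional on the p-value being taken from that output, on which the SAP is silent. This should be fixed before the Week 16 analysis; it does not call the planned method into question.

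**What to change.** In SAP 5.4.1.2, make the pooling call read `<modified dataset_t>`, which holds the log odds ratio and its log-scale standard error, and keep the single back-transformation that follows. Add one sentence stating that the one-sided p-values for H1 and H2 come from that pooled log-scale output. Test-run the corrected call before database lock, and confirm that equal response rates give an odds ratio near 1.

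The cost is one corrected reference, one sentence and a test run, with further code edits only if the call does not execute. No new data or analysis is needed.

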5.4.2 Secondary analysis

5.4.2.1 Analysis of binary (and categorical) data

Summary statistics for discrete variables will be presented in contingency tables and will include absolute and relative frequencies. If applicable, confidence intervals will be derived as well based on the score method including continuity correction [Newcombe (1998)]:

With z as $(1-\alpha/2)$ -quantile of the standard normal distribution (SAS: $z=\text{PROBIT}(1-\alpha/2)$), n as total number of subjects (i.e. number of subjects in the denominator), and p as estimated crude incidence (number of subjects with event / n) it is $q = 1 - p$

Then the lower limit is for $p > 0$, ($L = 0$ for $p = 0$),

$$L = \max \left(0, \frac{2np + z^2 - 1 - z\sqrt{z^2 - 2 - \frac{1}{n} + 4p(nq + 1)}}{2(n + z^2)} \right)$$

and the upper limit is for $p < 1$, ($U = 1$ for $p = 1$),

$$U = \min \left(1, \frac{2np + z^2 + 1 + z\sqrt{z^2 + 2 - \frac{1}{n} + 4p(nq - 1)}}{2(n + z^2)} \right).$$

For response variables (e.g. for IGA mod 2011 0 or 1, [REDACTED], PASI 90 and [REDACTED] response) the adjusted response rates (risk difference) including 95% confidence interval will be derived by visit.

For time courses of response variables, the point estimate at each time point including 95% confidence interval will be plotted.

5.4.2.2 Crude incidence and $100*(1-\alpha)\%$ confidence interval

For n subjects, each at risk to experience a certain event with probability π , the crude incidence is estimated as $p=x/n$, where x is the number of subjects with the event.

Absolute and relative frequencies will be displayed as well as 95% confidence interval for the relative frequency based on the score method including continuity correction (Newcombe 1998).

With z as $(1-\alpha/2)$ -quantile of the standard normal distribution (SAS: $z=\text{PROBIT}(1-\alpha/2)$), n as total number of subjects (i.e. number of subjects in the denominator), and p as estimated crude incidence (number of subjects with event / n) it is $q = 1 - p$.

Then the lower limit is

$$L = \max \left(0, \frac{2np + z^2 - 1 - z \sqrt{z^2 - 2 - \frac{1}{n} + 4p(nq + 1)}}{2(n + z^2)} \right)$$

and the upper limit is

$$U = \min \left(1, \frac{2np + z^2 + 1 + z \sqrt{z^2 + 2 - \frac{1}{n} + 4p(nq - 1)}}{2(n + z^2)} \right)$$

Note: if $p = 0$ then $L = 0$ and if $p = 1$ then $U = 1$.

If appropriate, an exact $100*(1-\alpha)\%$ confidence interval (Clopper-Pearson 1934) will be obtained by using the SAS procedure PROC FREQ with the EXACT BINOMIAL statement. However, the confidence interval derived via the score method including continuity correction will be the default in safety analyses.

5.4.2.3 Risk difference and $100*(1-\alpha)\%$ confidence interval

For an investigational drug group with n_1 subjects at risk, independent from the control group (e.g., placebo or comparator) with n_0 subjects at risk, of whom x_1 and x_0 experience a certain event, the risk difference is estimated as $p_1 - p_0$ with $p_1 = x_1/n_1$ and $p_0 = x_0/n_0$.

Exact unconditional confidence limits for the risk difference will be obtained with SAS procedure PROC FREQ and option RISKDIFF in the TABLES statement, specifying the RISKDIFF option also in the EXACT statement.

